# 13.8.4 Accrual Monitoring Stopping Rule

Patient accrual will be closely monitored by the investigators and study statistician on a biweekly basis. If the accrual rate falls below 50% of expected accrual rate, investigators will carefully review feedback from sites and consider taking measures to encourage patient enrollment, updating our accrual plan in Section 1.7 as needed.

# 13.9 Inclusion of Women and Minorities

This study will be available to all eligible patients, regardless of race or ethnic origin.

As African American women have been shown to demonstrate higher rates of moist desquamation, they would be expected to gain a substantial benefit from Mepitel Film.  Furthermore, as poor and Hispanic women have been shown to be more likely to receive a chest wall boost, this places them at high risk of more severe skin reactions.  As such, we will make a concerted effort to accrue 25% (or 54 of 216) of the total patients in this combined category. For that, we have a Health Disparities Committee Co-Chair on this protocol, to ensure a focused effort at achieving this important accrual goal of African American and Hispanic women. Furthermore, we will enlist NCI Community Oncology Research Program (NCORP) Principal Investigators who specialize in minority and underserved patient populations and we will activate the study at NCORP sites enriched in African American and Hispanic women receiving treatment for breast cancer.

Once our study meets its planned accrual goal, we will close it to further accrual, with the exception of accruing Hispanic and African American patients, with the plan of obtaining 25% (or 54) of the 216 total patients in this combined category. We have also included the stratification factor planned boost (yes; no) at the time of randomization to ensure balance across the arms. Within the 54 Hispanic and African American study population (due to randomization approximately 36 on Mepitel Film and 18 on institutional standard of care), we will estimate the proportion of acute grade 3+ radiation dermatitis, and skin and soft tissue fibrosis using NCI CTCAE v5.0 within each arm along with the corresponding two-sided 90% confidence interval. Assuming that the proportion of such events on the Mepitel Film arm is 10% and the proportion on the institutional standard of care arm is as low 45%, the lower bound of the two-sided 90%

confidence interval for the difference in proportions constitutes a clinically important difference (90% CI: 0.14, 0.56); furthermore, sample sizes of 18 and 36 produce a two-sided 90% confidence interval for the difference in population proportions with a width that is at most 0.42, i.e. assuming that the proportion of grade 3+ acute toxicity is 10% in the Mepitel Film arm and ranges from 45% to 70% in the institutional standard of care arm.

As part of our analysis plan, we will descriptively evaluate racial/ethnic and socioeconomic differences in our results. The area deprivation index (ADI), which is an existing measure of neighborhood socioeconomic disadvantage, is calculated based on an individual zip code+4 and will be used as a proxy for socioeconomic status; zip code+4 level ADI for the United States is publicly available. Although the study is not prospectively powered to detect interaction effects between arm and either race/ethnicity or socioeconomic status, we will explore through planned subgroup analyses whether the magnitude of the Mepitel Film effect, as measured by skin reaction severity and incidence of moist desquamation, differs in a clinically meaningful way across race/ethnicity categories or by socioeconomic status; skin reaction severity is measured by the patient- and provider-completed mRISRAS scores over time and moist desquamation is a component of the provider-completed mRISRAS (score > 0 on 0 [Normal skin] to 4 [Deep or red purple] point scale).

We are not aware of any evidence suggesting differential effects in other subsets defined by race or ethnicity. Expected sizes of race by ethnicity subsets for patients randomized to this study are shown in the table below.

	Ethnic Categories				
Racial Categories	Not Hispanic or Latino		Hispanic or Latino		Total
	Female	Male	Female	Male	1
American Indian/ Alaska Native	2	0	0	0	2
Asian	5	0	0	0	5
Native Hawaiian or Other Pacific Islander	2	0	0	0	2
Black or African American	35	0	0	0	35
White	144	2	19	0	165
More Than One Race	7	0	0	0	7
Total	195	2	19	0	216

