### 1.0 BACKGROUND

### 1.1 Introduction

Radiation therapy is an integral part of breast cancer treatment for many women and is associated with a unique toxicity profile. In recent years, technological improvements in radiation delivery systems have resulted in reduced doses to normal tissues. However, in women requiring post-mastectomy radiotherapy (PMRT), decreasing radiation dose delivered to the skin may not be desirable because the skin is considered part of the treatment target. Indeed, in PMRT the skin is often intentionally covered with bolus to ensure coverage of the dermis and dermal lymphatics. Amongst women undergoing PMRT, radiation dermatitis continues to be a widespread source of treatment-related morbidity.2 Acutely, radiation dermatitis manifests as moist desquamation in up to 73% of patients, grade 3+ pain in up to 32% of patients, pruritus, and nearly universal erythema. The acute skin reaction may compromise quality of life. Importantly, the acute toxicity of radiation dermatitis is correlated with the risk of long term sequelae. Severe acute toxicity may lead to consequential chronic effects including telangiectasias, hyperpigmentation, and, in extreme cases, ulceration and necrosis.  Severe skin toxicity may also lead to incomplete or interrupted treatment, which risks compromise of the oncologic outcomes, and could increase the risk of breast reconstructive complications, including reconstruction failure. 9,10 The etiology of radiation dermatitis is incompletely understood. There is wide variation in the severity of dermatitis between patients. suggesting that the etiology of severe radiation dermatitis is more complex than the dose to the skin or the volume of skin irradiated alone. Given the potential impact on treatment related morbidity and quality of life, a better understanding of the pathogenesis of radiation dermatitis and means of preventing this important complication of PMRT is needed.

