# 13.5.2 Analysis Plan for Secondary Endpoints

The first three secondary endpoints defined in Section 13.5.1 may provide supportive information about the prophylactic effect of the Mepitel Film on the primary endpoint. Stated differently, the first three secondary endpoints characterize prophylactic effects related to the primary endpoint but may extend our understanding of that effect. The collection of these three secondary endpoints constitutes a family of secondary endpoints. A gatekeeping statistical strategy will be used to control the Type I error rate at 0.05 across the primary and this secondary family of endpoints such that when an effect on the primary endpoint is demonstrated, this family of secondary endpoints will be examined and may contribute important supportive information about the effectiveness of the Mepitel Film.

A fixed-sequence strategy will be applied to this family of three secondary endpoints defined above. Provided the study's primary objective is achieved, a between-arm comparison will be made in the centralized, blinded provider-completed mRISRAS scores obtained from a blinded grading of the photographs taken at the end of radiation therapy. Notably, a panel of radiation oncology providers will perform the blinded, central review to grade the photographs. Each provider will independently score each photograph, and the average score will be calculated for each patient. The provider-completed mRISRAS score ranges from 0 to 24, obtained from summing the 4 individual scores, where higher scores correspond to increased radiation-induced skin reactions. For this first secondary endpoint,

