# APPENDIX VI MRISRAS- MODIFIED RADIATION INDUCED REACTION ASSESSMENT SCALE , 

# \*\*\*FOR HEALTHCARE PROFESSIONAL USE ONLY\*\*\*

#### INSTRUCTIONS FOR USE

- 1) Assess the patient at least once a week, recording the date and no. of fractions received.
- 2) Rate "Erythema" by recording the degree of color change.
- 3) Rate "Dry desquamation", "Moist desquamation", and "Necrosis" by evaluating the proportion (%) of the treatment area affected by that particular reaction.

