#### **Healthcare Professional Scale**

Erythema (E)	0		2	3	4
	(Normal skin)	(Dusky pink)	(Dull red)	(Brilliant red)	(Deep red-purple)
Dry desquamation (DD)	0 (Normal Skin)	1 (<25%)	2 (≥25- 50%)	3 (>50-75%)	4 (>75-100%)
Moist desquamation (MD)	0 (Normal Skin)	1.5 (<25%)	3.0 (≥25- 50%)	4.5 (>50-75%)	6.0 (>75-100%)
Necrosis (N)	0 (Normal Skin)	2.5 (<25%)	5 (≥25- 50%)	7.5 (>50-75%)	10 (>75-100%)

Note: See next page for patient completed portion.

INSTRUCTIONS: Please fill out the patient symptoms scale by selecting the option that best describes your condition for the given question.

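### Does the erythema scale printed in Section 13.9 spoil the moist desquamation outcome of the race/ethnicity and socioeconomic subgroup analyses?

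*Combined protocol and SAP*

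**What the plan says.** Section 13.9 explores whether the film effect differs by race/ethnicity or socioeconomic status. It uses two outcomes: skin reaction severity, measured by patient- and provider-completed mRISRAS scores over time, and incidence of moist desquamation. The second is defined in a parenthesis: "moist desquamation is a component of the provider-completed mRISRAS (score > 0 on 0 [Normal skin] to 4 [Deep or red purple] point scale". The section also states that the trial is not powered for these interactions.

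Appendix VI (Healthcare Professional Scale) has four items. Erythema runs from 0 to 4 by degree of colour change, with the top category labelled "Deep red-purple". A separate row, "Moist desquamation (MD)", is scored 0, 1.5, 3.0, 4.5 or 6.0. The instructions say to rate it "by evaluating the proportion (%) of the treatment area affected by that particular reaction".

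Section 13.5.2 gives the total: "The provider-completed mRISRAS score ranges from 0 to 24, obtained from summing the 4 individual scores". Section 1.1 describes "moist desquamation in up to 73% of patients" and "nearly universal erythema".

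**The concern.** The parenthesis names one item and describes the scale of another. Both the maximum (4) and the colour anchor are those of erythema, so a PDF reading fault does not explain it. Section 13.9 is also the only place in the statistical section that defines incidence of moist desquamation as an outcome.

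A programmer who took the printed scale as the guide to the item would count any erythema as moist desquamation. Section 1.1 expects erythema in almost everyone, so the event would be close to universal in both arms, and a film effect or subgroup difference on this outcome would be largely hidden. Higher moist desquamation rates in African American women are also among the reasons given for the goal of 54 African American and Hispanic patients, for whom accrual may stay open after the planned 216. An outcome tied to that rationale should not be ambiguous.

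**Working it through.** **1. Which scale does the moist desquamation item have?** Item maxima in Appendix VI: erythema 4, dry desquamation 4, moist desquamation 6, necrosis 10.

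- Sum: 4 + 4 + 6 + 10 = 24, which reproduces the 0 to 24 range in Section 13.5.2.
- With moist desquamation on 0 to 4: 4 + 4 + 4 + 10 = 22, which does not.

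The parenthesis in Section 13.9 is therefore the odd one out, and the rest of the protocol fixes the scale.

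**2. Does the wrong maximum change the event?** The rule is a score above 0. Category by category:

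| Category | Moist desquamation item | Event? | A 0 to 4 scale | Event? |
|---|---|---|---|---|
| Normal skin | 0 | No | 0 | No |
| 2nd | 1.5 | Yes | 1 | Yes |
| 3rd | 3.0 | Yes | 2 | Yes |
| 4th | 4.5 | Yes | 3 | Yes |
| 5th | 6.0 | Yes | 4 | Yes |

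The split is the same. An analyst who uses the named item gets the same event count whichever maximum is printed.

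**3. What if the erythema item were used by mistake?** Take 64 standard-care and 128 film patients (Section 13.3), and about 18 and 36 in the African American and Hispanic subgroup (Section 13.9). The power of a two-sided 5% comparison of two proportions is approximately

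Φ[(|p₁ − p₂| − 1.96·SE₀)/SE₁],

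where SE₀ uses the pooled proportion and SE₁ the separate ones.

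*Moist desquamation item.* As an illustration only, use the 66.7% and 43.8% of the post-mastectomy mometasone trial cited in Section 1.2; these are not film assumptions.

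- Difference: 66.7 − 43.8 = 22.9 points.
- Events: 64 × 0.667 ≈ 43 and 128 × 0.438 ≈ 56.
- Pooled proportion: (42.688 + 56.064)/192 = 0.514.
- SE₀ = √[0.514 × 0.486 × (1/64 + 1/128)] = 0.0765.
- SE₁ = √[0.667 × 0.333/64 + 0.438 × 0.562/128] = 0.0734.
- Power = Φ[(0.229 − 1.96 × 0.0765)/0.0734] = Φ(1.08) ≈ 0.86. At 18 and 36 patients it is about 0.35.

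*Erythema item.* The protocol gives no percentage, so these rates are assumed:

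| Standard care vs film | Difference | Power, 64 and 128 | Power, 18 and 36 |
|---|---|---|---|
| 99% vs 97% | 2 points | 0.10 | 0.04 |
| 100% vs 95% | 5 points | 0.42 | 0.08 |
| 95% vs 90% | 5 points | 0.19 | 0.07 |

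The normal approximation is rough this close to 100%, but the direction is plain: the outcome would lose most of its information. That happens only if the wrong item is used.

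**4. What lies outside the slip?** The severity outcome in Section 13.9 uses mRISRAS scores over time and does not depend on the parenthesis. The estimates in the 54 African American and Hispanic patients use CTCAE events, and the size of that group is justified by confidence-interval width for grade 3+ events. The primary endpoint (patient-completed scores, Section 13.4) and the gatekept secondary endpoints (Section 13.5) do not use this definition.

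**The case for a change.** The best case for a change is that an outcome definition should point to one variable. Here the item name and the scale point to different ones, there is no second definition in the statistical section to settle it, and the choice matters: step 3 shows a 22.9-point illustrative contrast shrinking to between 2 and 5 points under the wrong choice. The correction would be one line, would need no new data and would leave sample size and error control alone.

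The mismatch stands, and so does the cost of analysing the wrong item. What does not stand is that the text leads there. The sentence names moist desquamation; the scale is a description attached to that name. To reach the bad result, an analyst asked for moist desquamation would have to pass over the row that carries that label and take the one labelled erythema. Anyone who opens Appendix VI sees at once that the colour anchor is misplaced, and the 0 to 24 total settles any remaining doubt. Even in the bad case the subgroup analyses keep their severity outcome, so they would not be uninformative as a whole. The link to the accrual goal is also only partial: for poor and Hispanic women the reason given is more frequent chest wall boost.

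**Conclusion.** No change to the plan follows. Section 13.9 contains a clerical slip: the erythema range and anchor are printed beside the moist desquamation outcome. With the named item, the effect on the event count is zero, because a score above 0 marks the same four of five categories whatever maximum is printed. The loss of information in step 3 requires the erythema item to be analysed by mistake, and its size there rests on assumed erythema rates and on contrast figures borrowed from a steroid trial.

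The conclusion assumes that the analyst works from the item labels in Appendix VI, which is the natural reading. The analysis is exploratory and declared unpowered, and no confirmatory result depends on it. Tidying the parenthesis at the next routine update would do no harm, but it would alter nothing that the trial does or concludes.

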#### 14.0 CORRELATIVE AND COMPANION STUDIES

There will be one substudy and all patients are encouraged to participate.

# 14.1 Correlative Science (Alliance A221803-ST1)

# 14.1.1 Background

Radiation induced acute toxicities have been correlated with alterations of the microbiome in cancer treatment. In patients undergoing radiation to the abdomen or pelvis, alterations in the gut microbiome were found to correlate with the development of diarrhea. Observed changes in the microbiome include relative population differences in species as well as a decrease in overall microbial diversity. Changes in microbial diversity have also been documented in the oral microbiome during radiotherapy for head and neck cancer. The microbiome has also been linked to chemotherapy induced toxicities. Recent work completed at Mayo Clinic demonstrated that the microbiomes found in the breast parenchyma of non-cancer patients and breast cancer patients are distinct, raising the question of whether the background microbiome plays a role in carcinogenesis itself.

To date, the relationship of the skin microbiome to the development of radiation dermatitis is unknown. Radiation dermatitis is an inflammatory skin reaction. The relationship between the epithelial barrier, immune defense, and cutaneous microbiome has emerged as a key system for maintaining balance in the development of other inflammatory skin conditions. Alterations in the skin microbiome appear to play a role in the development and exacerbation of inflammatory skin conditions such as eczema and atopic dermatitis. In these conditions, severity of disease has been linked with increased colonization by Staphylococcus aureus (S. aureus). 79,80 Recently, commensal bacteria normally present on human skin were found to play a central role in controlling S. aureus through the release of antimicrobial peptides. Additionally, these commensal bacteria were found to be significantly reduced in atopic dermatitis. 81 Dilute sodium hypochlorite baths are effective at decreasing levels of pathogenic bacteria, and have demonstrated efficacy in reducing the severity of atopic dermatitis. 82-85 In addition, in pre-clinical mouse models, the use of topical hypochlorite (bleach) prior to radiation decreased the severity of acute radiation dermatitis and prevented skin ulceration. 86 Interestingly, case studies have found S. aureus to be a contributor to severe radiation dermatitis as well. Taken together, these data suggest that further study of the microbiome during acute radiation dermatitis may improve mechanistic understanding and identify future key therapeutic strategies.

This correlative study is designed to evaluate the changes that occur in the microbiome secondary to ionizing radiation alone as well as the ability of Mepitel Film to stabilize the skin microbiome and/or prevent superinfection, as we hypothesize. Given the vast number of cancer patients who experience radiation dermatitis, improvement in our understanding would be meaningful and encourage development of future novel interventions, with the potential to alleviate one of the most common radiation associated morbidities.

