### 7.2.1 Institutional Standard of Care Arm

Patients randomized to the standard of care arm will commence with conventionally fractionated PMRT, with skin management according to their institutional standard of care. Currently, there is no clear standard of care for reducing radiation dermatitis, and clinical practice varies widely across institutions. Patients randomized to this arm, should receive skin management as recommended by their treating physician. To help increase uniformity in the institutional standard of care arm, recommended guidelines for skin care are provided in Appendix IX. We recommend following these guidelines; however, it is not required for participation on this study. Specific skin care products will not be provided for the standard of care arm. Common interventions such as aqueous creams, petroleum ointments, aloe vera, acetic acid soaks, prescription interventions such as mometasone or lidocaine, and

wound care interventions such as Xeroform gauze or silvadene are all permitted. All products used throughout treatment will be recorded for future analyses (Appendix IV). The use of any applied prophylactic barriers including, but not limited to Mepitel Film, Mepitel One, Tegaderm, or Cavilon no sting Barrier Film, is prohibited on this trial. Therapeutic barrier interventions, such as Xeroform, are permitted to treat moist desquamation.

Acquisition of photographs is required for all patients and skin swabs (only for those who provide consent to participate in the optional sub-study). Both initial photos for all patients and skin swabs (for those who consent to participate in the optional correlative substudy) should be acquired no more than 3 days prior to the start of radiation therapy. Immediately upon completion of radiation therapy, the first set of post-treatment photographs and the second set of skin swabs should be acquired.

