Optional: Immediately following placement of the film, a warm blanket may be applied over Mepitel Film field and allowed to stay in place for 2-3 minutes. This may help with adherence and bring other unseen air bubbles to the surface.

Mepitel Film is typically applied using a patchwork approach. Based on the Mayo institutional experience, patients do not experience pain during application or removal of the Mepitel Film. If, after application of the Mepitel Film, the patient develops worsening pruritus or rash that, in the treating provider's opinion, is inconsistent with radiation related toxicity, and consistent with a film intolerance or allergy, the Mepitel Film may be removed. This is an unusual occurrence affecting less than 10% of patients, and typically happens within the first week following application. These patients should then be treated according to the institutional standard of care, and the film removal documented (see onstudy form in Medidata Rave). Should any patient develop pain secondary to film removal on this study, our recommendation is to proceed with conservative management with acetaminophen or ibuprofen as needed. If a patient develops moist desquamation under the Mepitel Film, the area of film immediately overlying the affected area of skin may be removed, and the treating provider should direct treatment of the moist desquamation according to their institutional standard of care. Mepitel Film should not be reapplied to

this area; however, it should remain in place over the remainder of the skin that is not affected by moist desquamation.

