# 8.1.2 Supportive Care

Patients should receive full supportive care while on this study. Patients randomized to the standard of care arm may use any topical intervention the treating provider deems appropriate, including, but not limited to aqueous creams, petroleum ointments, aloe vera, acetic acid soaks, prescription interventions such as mometasone or lidocaine, and wound care interventions such as Xeroform gauze or silvadene. All products used should be recorded (see Appendix IV).

Patients randomized to the Mepitel Film arm, should not apply any of the aforementioned products over the area where Mepitel Film is in place. For areas of adjacent skin not covered by Mepitel Film, any of the aforementioned products may be applied, and should be recorded (see Appendix IV). If, during the course of treatment, the Provider deems it medically necessary to remove the Mepitel Film, or if the patient is experiencing unacceptable adverse events or intolerance requiring the removal of Mepitel Film, full supportive care is recommended at the direction of the treating physician. This includes, but is not limited to, any of the aforementioned products.

Any patients who require oral medications for pain, should be offered appropriate symptom management according to their treating physician.

Any barrier films intended to be used prophylactically, in a similar manner to Mepitel Film, (i.e. Mepitel One, Cavilon no sting Barrier Film, etc.), are not allowed on this study. This does not include barriers used in the treatment of symptomatic dermatitis, such as Xeroform gauze, which are allowed for symptom management.

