# 14.2.2 Objectives

- a) To determine the impact of ionizing radiation on the skin microbiome, including quantitative analysis of *S. aureus*.
- b) To determine the effect of Mepitel Film on the skin microbiome, including quantitative analysis of *S. aureus*.
- c) To determine the impact of Mepitel Film on radiation-induced changes in the skin microbiome, including quantitative analysis of *S. aureus*.

d) To correlate the aforementioned alterations in the skin microbiome with the observed severity of radiation dermatitis.

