#### APPENDIX III PHOTOGRAPHY STANDARD BREAST PROTOCOL

# Standard Breast Protocol - Arms at side for first view

#### Alliance A221803

#### APPENDIX IV SKIN CARE FORM

Please record all skin care products patient is currently applying to treatment area (circle all that apply)

- a. Aqueous cream (i.e. Vanicream, Eucerin, etc.)
- b. Petroleum based ointments (Aquaphor, Vaseline, etc.)
- c. Aloe Vera
- d. Vinegar soaks
- e. Prescription creams/ointments (i.e. mometasone, lidocaine, topical antibiotics)
- f. Wound care products (i.e xeroform gauze, silvadene, etc.)

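### Control-arm microbiome change in A221803-ST1 reflects radiation under usual skin care, not radiation alone, and the Skin Care Form records antimicrobial use too coarsely to separate the two precisely

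*Combined protocol and SAP*

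**What the plan says.** Section 14.1.1 gives one purpose of the sub-study as evaluating "the changes that occur in the microbiome secondary to ionizing radiation alone". Objectives a to d in 14.2.2 cover the radiation effect (a), the film effect (b), "To determine the impact of Mepitel Film on radiation-induced changes in the skin microbiome" (c), and the correlation of these changes with dermatitis severity (d). Objectives a to c include quantification of *S. aureus*.

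On skin care, 7.2.1 says of the control arm that "wound care interventions such as Xeroform gauze or silvadene are all permitted", in a list that also names acetic acid soaks. Section 8.1.2 adds that controls "may use any topical intervention the treating provider deems appropriate". Patients in the film arm "should not apply any of the aforementioned products over the area where Mepitel Film is in place". There are exceptions: uncovered adjacent skin, skin after film removal for intolerance, and moist desquamation under film, where the overlying film may be removed and "the treating provider should direct treatment of the moist desquamation according to their institutional standard of care" (7.2.2, placement instructions). Appendix IX lists acetic acid soaks and silvadene among its recommendations for a moist skin reaction.

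Section 7.2.1 promises that all products used will be recorded for later analysis. The record is the Skin Care Form (Appendix IV), on which staff circle the categories currently being applied to the treatment area. Vinegar soaks are item d. Item e is "Prescription creams/ointments (i.e. mometasone, lidocaine, topical antibiotics". Item f is "Wound care products (i.e xeroform gauze, silvadene, etc".

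**The concern.** If control skin can receive antimicrobials and film-covered skin cannot, a difference in bacterial load between irradiated control skin and irradiated film-covered skin has two possible sources: the film, or the products used without it. Within the control arm, change from baseline likewise mixes radiation with product use. Because Appendix IX ties acetic acid and silvadene to moist reactions, use is also likely to rise with severity, and that exposes objective d to confounding by indication.

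The recording should be what allows these sources to be separated. It does so only in part. A circle on item e does not distinguish an antibiotic from a steroid or an anaesthetic, and a circle on item f does not distinguish silvadene from gauze. What is at stake is the mechanistic reading of the sub-study: whether a microbiome difference, or its absence, is put down to film, to radiation or to skin care.

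**Working it through.** The documents state no sample size, effect size or product-use rate for the sub-study, so there is no figure to reproduce. The check has two parts.

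**1. What each objective compares**

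- *Objective a, control arm:* irradiated skin at the end against baseline or the contralateral side. Products go on the treated side, so their effect is part of the contrast. In the film arm, irradiated film-covered skin against the contralateral film piece (7.2.2) gives a radiation contrast largely free of these products, but under film.
- *Objective b:* contralateral film against contralateral control skin. Both lie outside the treatment area, so this is largely protected.
- *Objective c:* irradiated film-covered skin against irradiated control skin. Product rules differ by arm.
- *Objective d:* severity against microbiome. Product use plausibly depends on severity.
- *Recording:* item d stands alone; items e and f are pooled. The form has no product name, site, frequency or last-use date, and no systemic antibiotic item. Appendix V captures wound infection needing oral or IV antibiotics, but only as a reconstruction complication. The form is due weekly before RT and at follow-up (5.0), while final swabs are taken at completion of RT (6.2). Footnote 3 of the calendar assigns the form to staff who apply film, so who completes it for controls is unclear.
- *Analysis:* Section 14 specifies no contrast, covariate or product handling. Product-category subgroups are planned only for mRISRAS endpoints (13.4.4, 13.5.3).

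That acetic acid and silvadene are antimicrobial is general pharmacology, not stated in the documents. Topical antibiotics are named on the form.

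**2. Illustrative size (all inputs assumed)**

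For a bacterial-load outcome with no true film effect and no product use in the film arm:

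shift in film minus control = share of controls exposed × size of product effect.

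With 19% and 49% exposed and a product effect of 0.5 SD: 0.19 × 0.5 = 0.095 and 0.49 × 0.5 = 0.245. A simulation with 2:1 allocation, a severity slope of 0.5 and product use rising with severity gives the following, in residual SD units. A positive value hides a reduction by film.

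| Use of d; e (antimicrobial share); f (antimicrobial share) | Controls exposed | Unadjusted | Form categories + severity | True antimicrobial flag + severity | Only controls with no d, e or f (share kept) |
|---|---|---|---|---|---|
| 0%; 50% (10%); 30% (50%) | 19.0% | 0.097 | 0.004 | 0.001 | 0.324 (40.1%) |
| 10%; 40% (10%); 20% (50%) | 20.9% | 0.104 | 0.008 | 0.002 | 0.272 (49.5%) |
| 20%; 50% (20%); 30% (50%) | 36.0% | 0.180 | 0.029 | 0.003 | 0.369 (36.1%) |
| 20%; 50% (50%); 30% (80%) | 49.3% | 0.241 | 0.048 | -0.004 | 0.353 (36.1%) |

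The unadjusted shift scales with the assumed product effect. At half that effect (0.25 SD) it is 0.19 × 0.25 = 0.05 to 0.49 × 0.25 = 0.12; at twice (1.0 SD) it is 0.19 to 0.49.

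The near-zero adjusted values assume that severity is measured without error and that the antimicrobial share within e and f does not vary with severity. If either fails, the residual is larger. The simulation also gives both arms the same severity. In the trial, severity is measured after randomisation and is what film is hypothesised to reduce (1.3), so adjusting for it would also remove any film effect acting through dermatitis. The last column shows that simply dropping exposed controls does worse than no adjustment, because those who remain have milder dermatitis.

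**The case against.** The strongest reply is that the sub-study can cope as it stands. Acetic acid soaks have their own item. The form asks about current use each week, so the last on-treatment form falls close to the final swab. Where moist desquamation affects the intended site, the routine swab moves to adjacent intact skin and the affected area gets a separate ninth swab (6.2.2), so routine swabs tend to avoid the skin most likely to be treated. Moist desquamation in the film arm may receive the same institutional care. Final swabs are taken at the end of radiation, whereas 1.4 places the frequent peak of dermatitis 7-14 days later. The sub-study is optional, and 2.4.1 frames it as collection for future analysis.

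All of this stands, and it rules out three stronger readings that a reader might infer:

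- *That adjustment is impossible.* Category-level adjustment is available and, in the illustration, removes most of the bias. It is imprecise and not pre-specified.
- *That the film-versus-control comparison is invalid.* As a randomised comparison of film with institutional care it is sound; only the attribution of a difference is mixed.
- *That 22-33% of control final swabs are affected.* Those figures come from the 43.8% and 66.7% moist desquamation rates in 1.2, with half of such patients assumed treated: 0.5 × 0.438 = 0.22 and 0.5 × 0.667 = 0.33. They count patients. With four of eight final swabs on the treated side, and bilateral radiation excluded (3.2.5), the share of swabs is at most 0.22 × 4/8 = 0.11 to 0.33 × 4/8 = 0.17 under the same assumptions, before allowing for the swab-site rule. The cited rates also carry no time point.

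The reply does not supply the missing detail on the form, or a rule for using it.

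**Conclusion.** The concern holds in a limited form. Control-arm change is radiation under institutional skin care, and the attribution in objectives a, c and d is mixed with topical product use. Objective b is largely protected. The form permits adjustment, but imprecisely, because items e and f pool antimicrobial with other products and no last-use date is recorded.

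The size of the bias cannot be derived from the documents. The illustrative 0.10-0.24 SD rests on assumed exposure and an assumed 0.5 SD product effect, with no product use in the film arm. The swab-site rule and the care allowed for moist desquamation in the film arm would both reduce it. If the products lower bacterial load, the shift is towards hiding a film effect and a severity link, but these same features make even the direction less certain.

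Severity is minor: no primary or secondary endpoint depends on this optional sub-study. It is worth acting on because product exposure not recorded around the swab cannot be reliably reconstructed later, and assays wait until accrual and final swab collection are complete (14.2.3).

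**What to change.** - **Appendix IV:** split item e into mometasone, lidocaine and topical antibiotic, and item f into Xeroform and silvadene. Add oral or IV antibiotics, and the date each product was last applied.
- **Section 5.0:** complete the form at both swab visits in both arms, and state who completes it for controls.
- **Section 14.1.1:** describe the aim as radiation under institutional skin care rather than radiation alone.
- **Section 14.1 analysis:** keep the full randomised comparison as the main contrast. Add one sensitivity analysis by antimicrobial exposure, with the look-back window fixed in advance. State that excluding exposed swabs conditions on a post-randomisation variable linked to severity, so it can only sit beside the main contrast.

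The cost is a slightly longer form and one extra analysis. Permitted care and swab procedures do not change. For any patients already swabbed, exposure would still rest on the present categories.
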